### 9.3.2. Follow-Up

Subjects will be followed from treatment start (or for comparator cohorts not defined by therapy: from an index date) until each outcome of interest, with death and emigration from Sweden treated as censoring events.

Some outcomes of interest in this study are thought to potentially occur at a higher rate while on drug, but that increased risk subsides after the drug is discontinued (ie, serious infections, herpes zoster, CV events, gastrointestinal (GI) perforation, progressive multifocal leukoencephalopathy (PML)). Those events will be evaluated over a risk window that includes time from drug initiation until 90 days after end of treatment. When a patient initiates a new therapy within the 90-day extension, the time and events during the overlapping period will be assigned to both treatments. The 90-day extension period is implemented in part to accommodate ongoing exposure to treatments with longer half-lives, and in part to ensure that any subclinical or undiagnosed illness at time of end of treatment is captured. As an additional sensitivity analysis for MACE, MI, serious infection, VTE, herpes zoster, PML, and gastrointestinal perforation events with a 90-day extension period applied after treatment discontinuation, if a new medication is started during the 90-day window after discontinuation of a previous medication, initiation of the new medication will stop the 90-day risk window, and any event prior to the new medication start will be assigned to the discontinued medication. Similarly, as part of the primary analysis, for malignancy and all-cause mortality events, a 90-day risk window will be applied to the censoring at switch approach (i.e., if a malignancy or death occurs in first 90 days after a patient has switched to a different therapy, follow-up time and the event will be attributed to prior therapy and not current therapy).

For non-melanoma skin cancer (NMSC), lung cancer, lymphoma and malignancies excluding NMSC, and all-cause mortality, the manifestation of which is expected to be delayed relative to the time of exposure, the outcomes will be evaluated using two different approaches, a once exposed always at risk approach as the primary analysis and a censor at switch approach as a secondary analysis. PML rates will also be described using this approach.

---

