Using this primary analytic approach, if neither tofacitinib nor bDMARDs cause an increased risk of malignancy both exposure cohort rates will reflect the background rates of malignancy from the time of index to the end of the study period and the comparative effect measure will indicate no difference in rates. If tofacitinib does cause an increased rate of malignancy, which is the effect we are most interested in detecting, a relatively higher rate will be observed in the tofacitinib exposed cohort. The once exposed always at risk approach is therefore able to detect an increased rate given the non-random switching expected to occur given use of bDMARDs prior to tofacitinib and is consistent with previous studies evaluating the risk of individual biologics. Additional analyses will be conducted to evaluate potential confounders and the impact of different latency assumptions as will be described in the statistical analysis plan (SAP). Sensitivity analyses will be conducted that restrict the bDMARD comparator cohort to patients who were never exposed to tofacitinib or other non-biologic advanced therapies and compare the characteristics of those bDMARD patients ever and never exposed to tofacitinib.

Secondary analyses that censor follow up time after a switch to a different treatment class will also be performed. Among patients indexed to a bDMARD cohort, follow up will begin at index and continue until the first of an event, switch to tofacitinib or other non-biologic advanced systemic therapy, loss to follow up, death, or study end date. Similarly, for tofacitinib, follow up will begin at index and continue until the first of an event, switch to a non-JAK inhibitor-based advanced systemic therapy, loss to follow up, death or study end date. While this approach eliminates the problem of double counting, it may not allow sufficient follow up time to allow for latent effects or detection and decreases the number of events included reducing the statistical power to detect a higher risk of malignancy in tofacitinib treated patients. However, under an assumption of no latency or a very short latent period as in an aggressive tumor promoter, this approach would detect an increased risk of disease on tofacitinib relative to the risk due to bDMARDs.

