#### 9.5. Study Size

All eligible patients in the Swedish registers will be included, with no upper limit on the sample size. The feasibility of more refined comparative analyses to evaluate safety concerns that adequately adjust for patient channeling and confounders will be assessed at an interim time point and after 7 years will be based on statistical power. Since the comparator groups will be a magnitude larger than the tofacitinib treated group, statistical power will be limited by the uptake of tofacitinib, which is difficult to estimate a priori. While the primary objective of the protocols is active surveillance, conducting quantitative, confounding controlled comparisons will depend on having a sufficient sample.

Table 2 and Table 3 below describe the power to detect a 2-fold difference in event rates between tofacitinib-initiators and bDMARD-initiators assuming the following:

- $\alpha=0.05$ ;
- 3 different bDMARD-treated patient population sizes (reflecting roughly range of EU registers):  $n=11100$ ,  $n=5050$ ,  $n=1650$ ;
- 4 different tofacitinib-treated patient population sizes:  $n=100$ ,  $n=250$ ,  $n=500$ ,  $n=1000$ ;
- Estimated rates on bDMARD of 30/1000 person years (PY) (eg, serious infection), 10/1000 PY (eg, malignancy excluding NMSC), and 6/1000 PY (eg, major adverse cardiovascular event (MACE)) based on previous analysis with registers (Pfizer, internal data);
- 7-year study period;
- Constant rate of accrual;
- 5% annual loss to follow up among tofacitinib-treated patients.

Additionally, Table 2 assumes a 0% annual rate of switching off tofacitinib, as would be true for a drug with very high persistence or for an analysis following the once exposed always at risk paradigm. Table 3 assumes a 30% annual rate of switching from tofacitinib to a bDMARD over the study period, as previously demonstrated in the EU for bDMARDs in Italy.

For an event with a rate of 30/1000 PY, such as serious infections, 250 patients would allow sufficient power to detect a 2-fold difference in rates between tofacitinib and bDMARD-exposed patients assuming very high persistence (Table 2), while 500 tofacitinib exposed patients would be nearly sufficient if 30% of tofacitinib treated patients switched off of tofacitinib annually.

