For an event with a rate of 10 cases per 1000 PY, such as malignancy excluding NMSC, a sample of 500 patients approaches 80% power in a medium (n=5050) to large (n=11,100) register when patient time continues to accrue after drug discontinuation (Table 2). It will be a challenge to achieve sufficient power in a register with fewer bDMARD exposed patients. Nonetheless, replication of a similar trend in an underpowered sample could be locally informative.

For an endpoint with an event rate of 6/1000 PY, such as MACE, even assuming high persistence (Table 2) a sample size of 1000 tofacitinib patients within a registry with more than 5000 bDMARD patients would be required to make well-powered comparison. In a scenario with a 30% annual rate of switching off of tofacitinib, 1000 tofacitinib treated patients and 11 100 bDMARD patients would only provide 40% power to detect a 2-fold difference (Table 3).

Prior to conducting any analyses, a feasibility assessment will be conducted to determine the approximate power of planned comparative analyses.

**Table 2. The Power To Detect A Two Fold Difference In Risk Among Tofacitinib Exposed Patients Compared With bDMARD Treated Register Patients Given Different Assumed Sample Sizes, alpha = 0.05, 5 Year Study With Uniform Accrual, 5% Loss To Follow Up Per Year In Tofacitinib Arm**

Number of tofacitinib exposed patients	~11100 bDMARD-treated patients	~5050 bDMARD-treated patients	~1650 bDMARD-treated patients
bDMARD rate ~ 30/1000 PY (eg, serious infections)			
100	0.46	0.45	0.44
250	0.92	0.91	0.88
500	1.00	1.00	0.9
1000	1.00	1.00	1.00
bDMARD rate ~10/1000 PY (eg, malignancy)			
100	0.11	0.12	0.12
250	0.38	0.38	0.36
500	0.75	0.73	0.66
1000	0.98	0.96	0.89
bDMARD rate ~ 6/1000 PY (eg, MACE)			
100	0.06	0.06	0.06
250	0.20	0.20	0.20
500	0.47	0.46	0.41
1000	0.83	0.79	0.68

090177e199570500\Approved\Approved On: 13-Feb-2022 20:25 (GMT)

**Table 3. The Power To Detect A Two Fold Difference In Risk Among Tofacitinib Exposed Patients Compared With bDMARD Treated Register Patients Given Different Assumed Sample Sizes, alpha = 0.05, 5 year Study With Uniform Accrual, 5% Loss To Follow Up Per Year In Tofacitinib Arm, 30% Switch From Tofacitinib to bDMARD Per Year**

Number of tofacitinib exposed patients	~11100 bDMARD-treated patients	~5050 bDMARD-treated patients	~1650 bDMARD-treated patients
bDMARD rate ~ 30/1000 PY (eg, serious infections)			
100	0.18	0.18	0.18
250	0.50	0.49	0.46
500	0.84	0.82	0.75
1000	0.99	0.98	0.93

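### Table 3 appears to keep tofacitinib switchers in the arm at the bDMARD event rate, so it understates power for the on-drug-plus-90-day and censor-at-switch analyses

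*Protocol*

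**What the plan says.** Section 9.5 says that Tables 2 and 3 "describe the power to detect a 2-fold difference in event rates between tofacitinib-initiators and bDMARD-initiators". The assumed bDMARD rates are 30, 10 "and 6/1000 PY (eg, major adverse cardiovascular event (MACE") per 1000 person-years. Table 2 has no switching, and the text links it to high persistence or to the once-exposed-always-at-risk analysis. "Table 3 assumes a 30% annual rate of switching from tofacitinib to a bDMARD over the study period"; the text does not say whether a switcher is censored or followed on.

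The captions read "alpha = 0.05, 5 Year Study With Uniform Accrual" (Table 2) and "5 year Study With Uniform Accrual, 5% Loss To Follow Up Per Year In Tofacitinib Arm, 30% Switch" (Table 3), whereas the assumption list gives a 7-year study period.

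On follow-up, Section 9.3.2 says of serious infections, CV events and similar outcomes: "Those events will be evaluated over a risk window that includes time from drug initiation until 90 days after end of treatment". For malignancy and mortality the primary analysis follows patients on after a switch. The secondary analysis ends tofacitinib follow-up at the first of an event, "switch to a non-JAK inhibitor-based advanced systemic therapy, loss to follow up, death or study end date".

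From Table 3 the text draws two conclusions: for MACE, that "1000 tofacitinib treated patients and 11 100 bDMARD patients would only provide 40% power to detect a 2-fold difference (Table 3"; and for serious infection, that 500 tofacitinib patients would fall just short. Sections 9.5 and 9.7.2 make the comparative analysis depend on statistical power.

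**The concern.** If a switcher's risk time ends at the switch, or 90 days later, switching costs person-time but the hazard ratio among those on drug remains 2. If the switcher instead stays in the arm at the bDMARD rate, the arm's average hazard ratio drifts towards 1 as follow-up lengthens, and power falls much further.

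Table 3 is the only table that models leaving tofacitinib. If it charges the on-drug analyses with a dilution they do not have, a feasibility assessment that starts from it would begin from figures that are too low. MACE is among the endpoints added after the June 2021 signal evaluation.

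**Working it through.** **Inputs (Section 9.5):** alpha 0.05 (sidedness not stated; two-sided assumed), rate ratio 2, uniform accrual over 5 years (the captions), 5% annual loss in the tofacitinib arm, 30% annual switching. Accrual is taken to span the whole study, with no loss among bDMARD patients.

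**Step 1: Table 3 against Table 2, without choosing a power formula.** With total exit hazard λ and uniform entry over 5 years, mean follow-up is (1/λ)[1 − (1 − e^(−5λ))/(5λ)].
- Loss only: λ = −ln 0.95 = 0.0513, giving 2.30 years.
- Loss plus censoring at switch: λ = 0.0513 − ln 0.70 = 0.0513 + 0.3567 = 0.408, giving 1.41 years.
- Ratio: 1.41/2.30 = 0.61 (about 0.65 if 30% is read as a simple hazard).

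The comparator is unchanged and in most cells far larger. N censored patients therefore carry roughly the information of 0.61N patients in Table 2.
- Serious infection, 500 patients: equivalent to about 306. Table 2 already prints 0.92/0.91/0.88 for 250, but Table 3 prints 0.84/0.82/0.75 for 500. More information cannot give less power.
- MACE, 1000 vs 11,100: equivalent to about 611. Linear interpolation in Table 2 gives 0.47 + (0.83 − 0.47) × 111/500 = 0.55. Table 3 prints 0.40.
- Malignancy, 1000 vs 11,100: 0.75 + (0.98 − 0.75) × 111/500 = 0.80. Table 3 prints 0.64.

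Censoring under the tables' own settings does not produce Table 3.

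**Step 2: what does produce it.** This is a Lakatos-type log-rank calculation. In each short interval D is the expected number of events, φ the ratio at risk (tofacitinib to bDMARD) and θ the average hazard ratio. Then U = ΣD[φθ/(1+φθ) − φ/(1+φ)], V0 = ΣDφ/(1+φ)² and V1 = ΣDφθ/(1+φθ)².

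With tofacitinib at twice the bDMARD rate, power = Φ((U − 1.96√V1)/√V0) and switchers kept at the bDMARD hazard, the quoted MACE cell comes out at 0.40-0.41, and 34 of 36 Table 3 cells agree within 2 points. Censoring at switch under the same formula matches 10 of 36. This variance arrangement is non-standard and matches only 22 of 36 Table 2 cells.

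A second set-up fits both tables better. Tofacitinib is at the listed rate and bDMARD at double, in quarterly steps, with the usual Φ((U − 1.96√V0)/√V1). With switchers kept, all 36 Table 3 cells agree within 1.5 points. Table 2 agrees within 2.3 points, apart from the cell printed 0.9. Censoring misses Table 3 by up to 26 points and moves MACE from 0.40 to about 0.60. The two set-ups differ on direction but agree on switchers.

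**Step 3: power for the planned analyses**, tofacitinib at twice the bDMARD rate, treatment ending at 30% per year. MACE, 1000 vs 11,100, 5 years:

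| Handling of switchers | Formula from Step 2 (first set-up) | Textbook Φ(U/√V0 − 1.96) | Simulated log-rank |
|---|---|---|---|
| Kept at bDMARD hazard | 0.40 | 0.57 | 0.54 |
| Drug + 90 days, tail hazard ratio 1 | 0.52 | 0.75 | 0.69 |
| Censored at switch | 0.55 | 0.79 | 0.70 |
| Drug + 90 days, tail hazard ratio 2 | 0.59 | 0.81 | 0.75 |

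Within each column the switcher assumption alone costs about 12 to 24 points. The rest of the gap between 0.40 and 0.7-0.8 comes from the formula. At 7 years the corrected ranges are 0.60-0.67, 0.81-0.87 and 0.72-0.81.

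Serious infection, 500 vs 5050, 5 years: the Step 2 formula gives 0.81 with switchers kept (printed 0.82) and 0.93-0.96 for drug plus 90 days. Simulation gives 0.95-0.97.

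**The case against.** Four points on the other side have weight.

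- **The mechanism is inferred.** Section 9.5 never states it. A one-sided censoring variant with the tofacitinib rate halved matches 31 of 36 Table 3 cells. It matches only 10 of 36 in Table 2, however, so it does not explain both tables. The inference is strong but not certain.
- **The MACE message largely survives.** A reader might infer that the protocol wrongly rules MACE infeasible. It makes no such ruling: it describes one scenario and defers to a feasibility assessment, which under Section 9.7.2 also weighs overlap of the patient populations. Corrected MACE power mostly stays below 80%, so the change is one of degree.
- **One planned analysis does keep switchers.** A reader might infer that Table 3 matches nothing in the plan. But the primary malignancy and mortality analysis follows patients on after a switch, and the schematic in Section 9.3.2 credits such a patient's later event to tofacitinib. If the effect ends at switching, the malignancy rows could serve as a pessimistic bound for that analysis, although Section 9.5 assigns that paradigm to Table 2.
- **The consequence is limited.** The study is descriptive, enrols all eligible patients, and the error is conservative.

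What stands against this is narrower: for serious infection, MACE and the censor-at-switch analysis, the printed figures do not describe the planned analysis.

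**Conclusion.** The point holds for the serious infection and MACE rows, and for the malignancy rows when read as the secondary analysis. Table 3 understates their power. At 5 years, MACE with 1000 vs 11,100 rises from 0.40 to about 0.52-0.59 on the reproducing formula and to about 0.7-0.8 by simulation or the textbook formula. Serious infection with 500 vs 5050 rises from 0.82 to about 0.95. The statement that 500 patients fall just short for serious infection is already too cautious for two of the three register sizes as printed (0.84 and 0.82).

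No single replacement figure for MACE is established, because the result depends on the formula, the hazard in the 90-day tail, the effect direction and the study length. It also assumes two-sided testing and treatment ending at the 30% switching rate. The documents do not support saying that MACE was declared infeasible, or that a corrected table would make it clearly well powered.

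**What to change.** - State in Section 9.5 how Table 3 handles switchers, which group has the higher rate, the power formula and sidedness, and one study length (captions 5 years, assumption list 7).
- Recompute the serious infection and MACE rows for drug plus 90 days, with tail hazard ratios 1 and 2, and the malignancy rows for censoring at switch. If a diluted malignancy row is kept, label it as a pessimistic bound for the once-exposed-always-at-risk analysis.
- Replace the MACE sentence and the sentence on 500 patients for serious infection with the recomputed figures, and carry these into the feasibility assessment.

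The cost is one rerun table and a few edited sentences, with no change to data or conduct. If stopping without a switch is also modelled, some figures will fall slightly.

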### 9.6. Data Management

This study analyzes data existing with the ongoing ARTIS register. The ARTIS researchers are responsible for the data management of this study. As previously described, health and demographic information within Sweden is collected in a series of registers with a high degree of completeness resulting from the mandatory and semi-automated registration of their data. Based on each Swedish resident's unique personal identification number, issued to all Swedish residents alive in 1947 or born/immigrated thereafter, linkage of data from different registers is possible. The registers are maintained by governmental bodies (the main registers used in this project are held by the National Board of Health and Welfare (Socialstyrelsen) and Statistics Sweden), who may perform data linkages and provide de-identified data for research purposes.

090177e199570500\Approved\Approved On: 13-Feb-2022 20:25 (GMT)

The data warehouses of ARTIS reside on restricted, double backed-up, servers at the Clinical Epidemiology unit at the Karolinska University Hospital Campus. All work with these data ware houses is done by trained staff in adherence with local guidelines on good programming and data management practices, and on archiving. Data, programs, and documents related to study reports will be maintained for a minimum of ten years.

## **9.7. Data Analysis**

All statistical analyses will be performed by ARTIS using Statistical Analysis Software (SAS) version 9.4 or later. Detailed methodology for any comparative analyses of data included in this study will be documented in a SAP, which will be dated, filed and maintained by the sponsor. The SAP may modify the plans outlined in the protocol; any major modifications of primary endpoint definitions or their analyses would be reflected in a protocol amendment.

### **9.7.1. Semi-Annual Reports**

Reports summarizing the rate of safety events of interest will be provided by ARTIS to Pfizer on a semi-annual basis, with tables corresponding to the template Appendix 1. These will provide data from SRQ/ARTIS on the patients treated with tofacitinib and rates “on drug” and “ever since treatment start”, but they will not contain comparator cohorts or adjusted comparisons.

### **9.7.2. Final Safety Report**

The feasibility of conducting a final comparative study will be evaluated at an interim time point and at 7-years of follow up based on statistical power and suitable overlap in patient populations in the exposure groups. The feasibility assessment, like the final report, will be conducted using safety events of interest identified through linkages with the patient, cancer and death registers, as appropriate. ARTIS will apply an ICD-code based algorithm to identify serious infections, GI perforations, herpes zoster, and CV events (MACE), in the Swedish patient register. Appendix 4 describes the algorithms used to identify these endpoints in ARTIS and relevant validation references, along with definitions used by other EU registers. The specific algorithms for defining those endpoints have not been validated, though the Swedish patient register has been validated several times (Ludvigsson 2011). The overall positive predictive value (PPV) of the inpatient diagnoses generally ranged from 85% to 95%. A regional validation study of hospitalized acute MI and stroke (components of the MACE endpoint) found positive predictive values of 96% and 94% respectively, in the period 1977 to 1987 (Lindblad, 1993). An ICD-9 code based algorithm applied to inpatient diagnoses of GI perforations in the US demonstrated high PPV (89.1-100) (Curtis, 2011). While the ICD algorithms used by ARTIS to define the endpoints of interest may not be validated, their use can be justified given the importance to contextualize the study results with historical findings. ARTIS has previously conducted and published studies of serious infections (Askling, 2007), PML (Arkema, 2012), and MACE (Michaud, 2016) events in RA patients.

The Swedish national register for contagious diseases, will serve as source of information on TB and other possibly serious contagious diseases for which there is a mandatory registration in Sweden. These reports will be based on a standardized analytical scheme, with some but limited flexibility to add additional endpoints and stratification, and will contain populated tables in line with the shells in Appendix 2. Whether these reports include formal comparisons of patients exposed to tofacitinib and bDMARDs will be determined a priori based on adequate power.

For these analyses, the exposure cohorts will be analyzed overall, by previous biologics use and monotherapy and combination therapy with concomitant conventional synthetic disease modifying antirheumatic drugs (csDMARDs). Increased risk of malignancy (excluding NMSC), MACE, MI, serious infection, VTE, herpes zoster, PML, and gastrointestinal perforation events, as well as an increase in mortality, in patients treated with a combination therapy with MTX specifically will be described if sample sizes are sufficient, in the interim and final reports. These and potentially other agreed upon strata will be determined a priori and included in SAP filed with Sponsor. The general analytic approach will be descriptive and include rates of events of interest within stratified treatment cohorts. Data will be presented as number of events, crude and age/sex-standardized incidence rates.

Any final comparative report will adjust for differences in severity of disease and other confounders will be completed using appropriate multivariate, propensity score matching, or inverse probability weighting. The final report will also evaluate the rates of safety events of interest within the elderly. The outcomes reported will include hospitalized infections, OI, herpes zoster, fractures, hepatitis, GI perforations, malignancies, CV events, and all-cause mortality, with subgroupings and selected additional outcomes per agreement. HRs from multivariable Cox regressions adjusting for sex, age, year of treatment start, treatment history, disease severity, comorbidities, and other potential confounders to be agreed upon by ARTIS and the Sponsor and defined in an SAP prior to analysis. The final SAP will also specify an ICD-algorithm harmonised with other registers conducting similar analyses for serious infections, CV events, GI perforations, and herpes zoster (HZ).

Any comparative safety reports will leverage data linkages to obtain data on all comorbidities that have led to hospitalization, cancer or death. Data on malformations and perinatal morbidities and mortality can also be obtained from the birth register.

For lymphoma, incidence rates will be stratified by lymphoma subtypes; not limited but including non-Hodgkin lymphoma (NHL), Hodgkin lymphoma, chronic lymphatic leukemia. Similarly, CV event rates will be stratified by type of event (e.g. myocardial infarction (MI), MACE, serious congestive heart failure). Further, for the outcomes of MI and MACE, incidence rates of the safety events of interest will be stratified by patients with  $\geq 1$  CV risk factors versus no CV risk factors. The rates of safety events of interest, including infections, MACE, MI, and malignancies excluding NMSC, will also be evaluated within the elderly aged  $\geq 65$  years. Descriptive data will be presented in the interim reports. Likewise, VTE event rates will be stratified by type of event (DVT and PE). Further, for the outcomes of VTE, incidence rates of the safety events of interest will be stratified by patients with  $\geq 1$  VTE risk factors versus no VTE risk factors.

At study completion, all descriptive and comparative data analyses will be presented in the final report.

If feasible, stratified analyses to estimate the incidence rates for VTE stratified by time periods defined by the changes in the SmPC for tofacitinib use in patients with VTE risk factors will also be conducted (i.e., time period prior to 31 January 2020 vs. time period after 31 January 2020). Additionally, if feasible, stratification of the incidence rates for malignancy excluding NMSC, lung cancer, lymphoma, MACE and MI by time periods defined by changes in the SmPC for use in patients with malignancy and CV risk factors will be conducted (i.e. time period after June 2021).

Meta-analytic methods that attempt to combine the results of this study with results from other participating European registers will be used to summarize the findings across studies. A quantitative meta-analysis would permit an estimate of an average effect across the studies with more statistical power than the individual studies, provided a formal evaluation did not reveal substantial heterogeneity. Meta-analysis may reveal between-study heterogeneity such that a subset of more comparable studies could be included in a single estimate. Heterogeneity may be expected, for example due to differences in local prescribing practices, patient populations, competing risks, and prevalence of comorbidities and risk factors. Such heterogeneity would exist even if the coding for endpoint definitions and reporting could be harmonized across registers. In the presence of such heterogeneity, pooling across the registers is not informative as the generalizability of such an estimate is unknown. Pending feasibility of comparative analysis, meta-analytic methods will be determined a priori and described in an approved SAP.

